a. Describe precautions that will be taken to avoid risks and the means for monitoring to detect risks.

We will use the standard precautions for placement of regional blocks which include sterile technique and ultrasound-guided placement. Patients will be monitored during regional block placement with pulse oximetry, EKG, non-invasive blood pressure and capnograph monitors. Regional block will be performed under routine sterile conditions.

A data and safety monitoring plan will be implemented by Drs. [name] and [name] to ensure that there are no changes in the risk/benefit ratio during the course of the study and that confidentiality of research data is maintained. This will be achieved by close following of study participants to screen for adverse events and interim results analysis during data collection phase. Investigators and study personnel will meet either electronically or in person, monthly (more often if needed) during active participant enrollment to discuss the study (e.g., study goals and modifications of those goals; subject recruitment and completion; progress in data coding and analysis; documentation, identification of adverse events or research subject complaints; violations of confidentiality) and address any issues or concerns at that time. A DSMB committee will review outcomes and any adverse events as they occur or every six months (if no adverse or reportable events). The DSMB consists of [name], [name], [name], [name].

If the protocol involves drugs or devices skip Items 20.b. and 20.c. and go to Item 21. Instead include this information in the [Drug Review Sheet](#) or [Device Review Sheet](#), as applicable.

b. If hazards occur to an individual participant, describe (i) the criteria that will be used to decide whether that participant should be removed from the protocol; (ii) the procedure for removing such participants when necessary to protect their rights and welfare; and (iii) any special procedures, precautions, or follow-up that will be used to ensure the safety of other currently enrolled participants. **If the patient meets the inclusion criteria, the block will be administered. Any negative event will be evaluated and treated as per standard of care. Each patient will have immediate follow-up evaluation performed by the PI or co-investigators to look for safety concerns.**

c. If hazards occur that might make the risks of participation outweigh the benefits for all participants, describe (i) the criteria that will be used to stop or end the entire protocol and (ii) any special procedures, precautions, or follow-up that will be used to ensure the safety of currently enrolled participants.

Quadratus lumborum blocks are described for perioperative analgesia for abdominal procedures and hip arthroplasty. We do not anticipate additional risks for the patients who choose to participate in the study, as compared to other patients who undergo truncal blocks.

A data and safety monitoring plan will be implemented by Drs. [name] and [name] to ensure that there are no changes in the risk/benefit ratio during the course of the study and that confidentiality of research data is maintained. This will be achieved by close following of study participants to screen for adverse events and interim results analysis during data collection phase. Investigators and study personnel as well as the DSMB (consisting of clinicians and scientists: [name], [name], [name], [name]) will meet either electronically or in person, to evaluate any adverse or reportable event every six months during active participant enrollment.

21. Informed Consent

- a. Do you plan to obtain informed consent for this protocol? Yes No
If Yes, complete the items below.
If No, complete and include the [Waiver of Informed Consent](#) or [Waiver of Authorization and Informed Consent](#), as applicable.
- b. Do you plan to document informed consent (obtain signatures) for this protocol? Yes No
If Yes, complete the items below.
If No, complete the items below and include the [Waiver of Informed Consent Documentation](#).
- c. How will consent be obtained? **The interviewing investigator will confirm eligibility and absence of any exclusionary criteria. Details of the study (including risks) will be explained to prospective participant to their satisfaction and consent forms will then be signed.**

Informed consent will be obtained electronically using REDCap, a HIPAA compliant application. The UAB IRB has approved the use of REDCap for e-consents and HIPAA Authorization in other studies in the Department of Anesthesiology. The electronic Informed Consent (e-consent or eIC) is similar to the traditional paper-based Informed Consent in that it provides the potential subject with sufficient information about the research project to allow for an informed decision about the subject's voluntary participation in the study. The workflow for the consenting process will be the same as for the traditional paper consent/authorization. The Principal Investigator or study staff trained in providing Informed Consent will be present during the entire consenting process. The study staff will verbally present the study as with the paper form and then log into REDCap using unique credentials and a secure password. The subject will be presented with a touch screen enabled tablet (or paper copy if the subject requests). The subject will be allowed to read the e-consent and then ask the study personnel questions about the material as well as address any follow-up questions. Once the subject is fully satisfied that they have an understanding of the information being presented in the Informed Consent, the patient (or legally authorized representative) will use an electronic pen to provide a "wet signature" verifying their consent to participate in the study (signed in the presence of study personnel). The computer will provide time/date stamps as the time of the signature. The prospective subject will also digitally sign the HIPAA Authorization. In the case of the involvement of a legally authorized representative, the representative will digitally sign as well as type the printed name and their relationship to the participant using the attached keyboard. All versions of the IRB approved versions of the Informed Consent will be archived and easily retrievable. There some patients who may not feel comfortable with electronic systems, or have poor eyesight or impaired motor skills, so the patient will always have the option to using paper-based informed consents. In this case, the signed paper consent form will be scanned and entered into REDCap as an attached document. If requested, study personnel will provide assistance in the navigation of the e-consent.

d. Who will conduct the consent interview? **The Principal Investigator or study staff trained in providing Informed Consent will consent the patient and be present during the entire consenting process. All study staff will be fully trained and approved by the IRB.**

- e. Who are the persons who will provide consent, permission, and/or assent? **The patient or their Legally Authorized Representative (LAR)**
- f. What steps will be taken to minimize the possibility of coercion or undue influence? **Participation is voluntary and the potential participant will have every opportunity to ask any questions and raise any concerns and have those issues addressed to their satisfaction prior to obtaining and documenting consent.**
- g. What language will the prospective participant and the legally authorized representative understand? **English**
- h. What language will be used to obtain consent? **English**
- i. If any potential participants will be, or will have been, in a stressful, painful, or drugged condition before or during the consent process, describe the precautions proposed to overcome the effect of the condition on the consent process. If not, enter "None." **None**
- j. If any protocol-specific instruments will be used in the consenting process, such as supplemental handouts, videos, or websites, describe these here and provide a copy of each. If not, enter "None." **None**
- k. How long will participants have between the time they are told about the protocol and the time they must decide whether to enroll? If not 24 hours or more, describe the proposed time interval and why the 24-hour minimum is neither feasible nor practical.
The consent process will begin during the potential participant's pre-operative visits to UAB. Participants may not have more than 24 hours after learning of the study before documenting their consent to participate, but they will have additional days following screening and documentation of consent before implementation of any study specific procedures.

22. Procedures to Protect Privacy

Describe how you will protect the privacy interest of the participants. Include how you will make sure others cannot overhear your conversation with potential participants and that individuals will not be publicly identified or embarrassed. **Privacy will be ensured at all times. Conversations with potential participants will be conducted privately, usually in an exam room with a closed door to prevent others from overhearing the conversation. Individuals will not be publicly identified or embarrassed.**

23. Procedures to Maintain Confidentiality

a. Describe how you will store research data to maintain confidentiality (both paper records and electronic data), including how access is limited. If data will be stored electronically anywhere other than a server maintained centrally by UAB, identify the department and all computer systems used to store protocol-related data. **Participant data will be stored on a password-protected server maintained for human subject's research purposes by the UAB Department of Anesthesiology. Access to this particular system is restricted to only approved members of the research team. The list of patients participating in the study, including their medical record numbers and dates of surgery, will be kept separately in a folder with access restricted to staff approved to access patient data. Access to the data will be terminated after final data analysis. Any original paper records may be scanned and stored on the above mentioned departmental server and then shredded after they have been transferred to the password-protected computer system. Signed Informed Consents will be retained for at least 3 years after closure of this study.**

- b. Will any data from this protocol be given to any person, including the subject, or any group, including coordinating centers and sponsors? Yes No

If Yes, complete i-iii.

- i. Who will receive the data? **Information will be shared with the UAB Anesthesiology faculty and residents, and other entities within the UAB Health System for quality improvement. Information may be presented at scientific meetings, conferences or may be published.**
- ii. What data will be shared? **Findings from study. Information regarding participant demographics will only be presented in aggregate form – age, sex, race, educational level, ASA (American Society of Anesthesiologists) status. . Additionally, results obtained from the study may be shared, including VAS scores for pain and need for rescue pain medication.**
- iii. How will the data be identified, coded, etc.? **Information will be de-identified and will be presented in aggregate form. None of the 18 HIPAA Identifiers will be disclosed**

24. Genomic Data Sharing (GDS)

Researchers who collect genomic data as part of a NIH grant funded after January 25, 2008 may be required to submit those data to a NIH database for broad scientific sharing. See [Genomic Data Sharing](#) in the IRB Guidebook for more information.

- a. Does this protocol involve the proposed submission of genetic data into genomic repositories created to share genetic information for research purposes? Yes No

- b. Will UAB be uploading the final genomic data to the central repository (e.g., dbGaP)? Yes No

If Yes to both a and b, submit a Detailed Data Sharing Plan to the IRB for review. This plan should include any known data use limitations and indicate whether aggregate-level data are appropriate for general research use. For guidance see the [NIH Genomic Data Sharing Policy](#).

- c. Submit a copy of the NIH Institutional Certification Form.

To determine which certification form to include, answer i-ii.

- i. Was this protocol funded prior to January 25, 2015? Yes No

- If yes, and consent will be obtained, submit the [Extramural Institutional Certification - Before January 25 - With Consent](#).
- If yes, and consent will not be obtained, submit the [Extramural Institutional Certification - Before January 25 - Without Consent](#).

- ii. Was this protocol funded after January 25, 2015? Yes No

- If yes, submit the [Extramural Institutional Certification - After January 25](#).

25. Additional Information

In the space below, provide any additional information that you believe may help the IRB review the proposed research, or enter "None." **None**

References:

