(Check and describe all that apply)
(If subaward, list both the funding source and the institution receiving the direct award)

- Gov't Agency or Agencies—Agency name(s): _____
 - Department of Defense (DoD): Identify DoD component: _____
 - Department of Energy (DOE)
 - Department of Justice (DOJ)
 - Department of Education

- NIH Cooperative Group Trial - Group name: _____
- Private Nonprofit (e.g., Foundation) - Name: _____
- Industry, investigator-initiated - Name: _____

Describe the funding arrangement: _____

NOTE: *The UAB IRB typically only reviews industry-sponsored protocols that are investigator initiated or when the protocol qualifies for expedited review or involves gene therapy.*

- UAB Departmental/Division Funds—Specify: _____

5. Locations Involved

a. Indicate all performance sites that will provide space, services, or facilities for the conduct of this protocol.

- UAB Hospital
- UAB Hospital - Highlands
- The Kirklin Clinic of UAB Hospital
- The Kirklin Clinic at Acton Road
- UAB Callahan Eye Hospital
- UAB Clinical Research Unit
- Children's of Alabama
- Birmingham Veterans Affairs Medical Center
- Jefferson County Department of Health
- Other (i.e., any performance site not listed above, including those covered by subawards related to this protocol) - Describe:

NOTE: *Documentation of IRB approvals from sites receiving subawards must be received by the UAB OIRB before funding will be released for that subaward.*

b. Describe the space, service, or facilities available for the conduct of the research in the performance sites listed in Item 5.a (For research on UAB campus, include building names): **The patients will be recruited and consented in their private rooms in the preoperative area of UAB Highlands. After enrollment and randomization, they will move to the block area that is well-equipped for placement of regional anesthesia techniques.**

c. Is this protocol a clinical trial requiring clinical services at one of the performance sites listed in Item 5.a above? Yes No

If Yes, will any of the services be billed to either participants/their insurance or to the study account through the Hospital Billing Office (PFS) or the HSF Billing Office (MSO)? Yes No

If Yes, submit a Full Fiscal Approval Process (FAP)-designated unit submission to s complete a FAP submission and send to [contact]. For more on the UAB FAP requirements, go to [FAP - SiteMinder Processes](#).

d. Is this a field study? Yes No

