- e. If participants will comprise more than one group or stratification, describe each group (e.g., treatment/intervention, placebo, controls, sham treatment) **and** provide the number of participants anticipated in each group.

Upon enrollment in the study, participants will be randomized 1:1 to either the investigational group (“Quadratus Lumborum Block” group) or the control group (“No Block” group). Participants will be randomized using a random number generator.

- f. Indicate which, if any, of the special populations listed below will be involved in the protocol. Include the Special Populations Review Form (SPRF) if indicated.
- Pregnant Women: Attach [SPRF—Pregnant Women, Fetuses, Neonates/Nonviable Neonates](#)
 - Fetuses: Attach [SPRF—Pregnant Women, Fetuses, Neonates/Nonviable Neonates](#)
 - Neonates/Nonviable Neonates: [SPRF—Pregnant Women, Fetuses, Neonates/Nonviable Neonates](#)

- Prisoners: Attach [SPRF—Prisoners](#)
- Minors (<18 years old): Attach [SPRF—Minors](#)
- Employees or students at institution where research conducted
- Persons who are temporarily decisionally impaired
- Persons who are permanently decisionally impaired
- Non-English Speakers

For each box checked, describe why the group is included and the additional protections provided to protect the rights and welfare of these participants who are vulnerable to coercion: Employees and students are eligible to participate. The suggested language has been included in the informed consent document to fully disclose that this project is separate from the expectations and their relationship with UAB as an employee or student.

g. List any persons other than those directly involved in the protocol who will be at risk. If none, enter "None": **None**

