h. Describe the recruitment process (e.g., medical record review, referrals, letter of invitation, existing patients) that will be used to seek potential participants (e.g., individuals, records, specimens). Research recruitment by non-treating physicians/staff may require completion of [Partial Waiver of Authorization for Recruitment/Screening](#). **Days to weeks prior to total hip arthroplasty, patients report to the Highlands Preoperative Assessment Clinic (HPAC) for standard of care preoperative evaluation and examination and preoperative testing, tailored to patient comorbidities. This is not a service that will be billed additionally for study participants, as it is standard of care for all total hip arthroplasty patients, regardless of participation in the study. During their HPAC visit, patients that may be eligible for the study will be given a "Patient Information Sheet," describing the study. On the day of surgery, patients will be seen in the preoperative holding area and enrolled in the study if they choose.**

All surgeons who perform total hip arthroplasty have requested for their patients to have QLB, at the discretion of the anesthesiologist.

i. If you will use recruitment materials (e.g., advertisements, flyers, letters) to reach potential participants, attach a copy of each item. If not, identify the source (e.g., IRB Protocol Number for approved databases) from which you will recruit participants. **N/A**

j. Describe the screening process/procedures for potential participants.

Study personnel will confirm eligibility requirements using a standardized eligibility checklist. This will be completed by the PI or another member of the research team prior to consenting and enrolling subjects in the study. This eligibility screening will occur in the preoperative holding area where each patient is in a private room. We have attached the Partial HIPAA Waiver for Recruitment and Screening.

All surgeons who perform total hip arthroplasty have requested for their patients to have QLB, at the discretion of the anesthesiologist.

17. Protocol Procedures, Methods, and Duration - in nontechnical, lay language

Describe the procedures for all aspects of your protocol. Tell us what you are doing.

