A. Participants in the study will be randomly assigned to either receive the pain block ("block group") or not ("control group"). The patient will be blinded and thus unaware of the group that they have been assigned. The patients are receiving sedation, including fentanyl and midazolam, an amnestic, prior to ultrasound scanning and +/- block placement. The amnestic properties of sedation will serve as blinding for the procedure. In the postoperative survey, we

ask the patients which group they believe they were in, which will help assess the adequacy of the blinding.

- a. **Block group: Subjects that are in the block group will receive the pain block while they are in pre-operative holding. The block will be administered as follows:**
 - i. **The patient will be placed on their side. Standard of care noninvasive monitors will be used, and oxygen will be given by nasal cannula. Midazolam and fentanyl will be given to patient comfort. Note: midazolam and fentanyl are provided to all patients who are receiving this surgery and is not part of this research project. The timing of the delivery of this medication may differ than standard of care, but the doses and indications are the same. Skin will be prepped and draped as per standard of care.**
 - ii. **Using ultrasound guidance, we will locate the appropriate space for the block. We will first inject numbing medication called lidocaine under the patient's skin (1-2 mL of 1% lidocaine; 10-20 mg). Then, we will inject another numbing medication called bupivacaine (30 mL of 0.25% bupivacaine with 1:400,000 epinephrine; 75 mg bupivacaine and 75 mcg epinephrine) between muscles using a syringe and needle.**
 - iii. **After the block is placed, patients will have their surgery performed.**
- b. **Control group: Patients randomized to the control group will be treated in the same manner (as described in section "i" above) as those randomized to the block group. The ultrasound probe will be used to identify the quadratus lumborum muscle, similar to patients in the block group. However, no local anesthetic will be injected.**

B. Postoperative data will be collected for both groups by a blinded study team member listed on this protocol.

- a. **Post-operative data that will be collected is listed in the attached Case Report Form.**
- b. **Information obtained from the patient will be collected using the attached Patient Interview Script.**
- c. **Patient will be followed up until nerve block resolves.**

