- d. **The hours from block placement until hospital discharge will be calculated.**

b. What is the probable length of time required for the entire protocol (i.e., recruitment through data analysis to study closure)? **One year.**

c. What is the total amount of time each participant will be involved? **Each participant will be involved in the study for approximately 48 hours. Each procedure time period is listed below.**

d. If different phases are involved, what is the duration of each phase in which the participants will be involved? If no phases are involved, enter "None." **None**

e. List the procedures, the length of time the procedure takes, the total # of times the procedure is performed, and indicate whether each is performed solely for research or would already be performed for treatment or diagnostic purposes (routine care) for the population.

-Insert additional table rows as needed.

-If procedure is sometimes research and sometimes routine care, include on separate lines with number of times as each.

Procedure	Length of Time Required of Participants	Frequency of Repetition	Research (Res) – OR- Routine Care
Pre-surgical Evaluation on the day of surgery	30 minutes	once	 Res  Routine
Randomization on day of surgery	5 minutes	Once	 Res  Routine
Placement of block	Approximately 30 min.	Once	 Res  Routine
Post Anesthesia Care Unit (PACU) assessment	10 minutes	Once	 Res  Routine
First postoperative assessment survey (approximately 24 hours after surgery)	10 minutes	Once	 Res  Routine
Second postoperative assessment survey (approximately 48 hours after surgery)	10 minutes	Once	 Res  Routine

- f. Will an interview script or questionnaire be used? Yes No
If Yes, attach a copy.
- g. Will participants incur any costs as a result of their participation? Yes No
If Yes, describe the reason for and amount of each foreseeable cost. _____
- h. Will participants be compensated? Yes No
If Yes, complete i-v.
i. Type: (e.g., cash, check, gift card, merchandise): _____

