General Data Analysis Plan: All demographic and clinical variables with continuous measures will be expressed as means and standard deviations; categorical factors will be expressed as proportions. For non-normal data, the medians and inter quartile ranges will be displayed. The distribution of the continuous factors will be examined using the Kolmogorov-Smirnov test. For data that are normally distributed, the one-way ANOVA and Student's t-test will be used to compare groups of data. For data that are not normally distributed, the Kruskal-Wallis and Mann-Whitney tests will be used for comparisons. Chi-square and Fisher's exact tests will be used to analyze categorical data. For all comparisons, a value of $p < 0.05$ will be considered statistically significant.

Primary Outcome Analysis: Statistical analyses will be performed using SAS for Windows, version 9.2. Student's t-test will be used to compare post-operative pain scores for investigational and control subjects. Linear regression will be also be used to test the relationship between pain scores and regional anesthetic technique, while controlling for relevant clinical and demographic variables. Distance of first ambulation will be analyzed using Cox proportional-hazards model. Student's t-test will be used to compare patient and surgeon satisfaction.

Statistical Power and Sample Size Estimates : Sample size (50 each group) was determined using a Cohen's d table assuming a mean pain VAS score of 8 (SD = 3) on a scale of 0-10 for control subjects. A difference of VAS score of 3 between two study groups will be clinically relevant. A sample of 100 participants (50 patients per group) will have approximately 95% power to detect a reduction in pain score difference of 3 with significance level alpha of 0.05. We will perform an interim analysis after 50 patients have completed the study (25 patients in each group).

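### Allocation is made before the sedation and scan that both arms share, although it is not needed until the injections; with no analysis set defined, this leaves room for arm-aware sedation and scan judgements and for one-sided exclusions

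*Combined protocol and SAP*

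**What the plan says.** **Timing of allocation.** Item 5.b states: "After enrollment and randomization, they will move to the block area that is well-equipped for placement of regional anesthesia techniques". Item 16.e ties allocation to enrollment: "Upon enrollment in the study, participants will be randomized 1:1 to either the investigational group"; the only further detail it gives is that a random number generator is used. The Item 17.e table has a 5-minute row, "Randomization on day of surgery", placed above the row for the block.

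**Shared steps.** Item 17, part A, says: "The patients are receiving sedation, including fentanyl and midazolam, an amnestic, prior to ultrasound scanning and +/- block placement". Controls are handled as in the block group for positioning, monitoring, oxygen, sedation adjusted to comfort, and skin preparation. They are also scanned: "The ultrasound probe will be used to identify the quadratus lumborum muscle, similar to patients in the block group". The arms separate at the next sentence: "However, no local anesthetic will be injected".

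**Screening.** Item 16.j describes an eligibility checklist: "This will be completed by the PI or another member of the research team prior to consenting and enrolling subjects in the study". The criteria in Item 16.d include nothing about the scan.

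**Numbers and analysis.** Item 16.a enrolls 100. The power paragraph of the Statistical Considerations says: "A sample of 100 participants (50 patients per group) will have approximately 95% power". That section defines no analysis set, missing-data rule, replacement rule or dropout allowance, and it counts the interim analysis in patients who have completed the study. Item 20.b says that patients who meet the inclusion criteria get the block; it has no rule for a block that cannot be placed.

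**The concern.** Two things follow from allocating before the shared steps.

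1. **Knowledge of the arm.** Patient blinding rests on the amnestic effect of sedation, and the amount of sedation is discretionary. The plan blinds the patient and the person collecting postoperative data, but nothing withholds the allocation from staff who sedate and scan. The depth of sedation, and the decision that a scan is or is not adequate, can therefore be made by someone who knows the arm.

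2. **An event that matters in one arm only.** If the muscle cannot be identified, a block patient goes untreated, while a control with the same anatomy carries on as assigned. With no analysis set defined, an analyst could drop the untreated block patients. That would compare a block group selected for favourable anatomy with an unselected control group.

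Both arise from the order of steps, and the order can be changed because the allocation is not used until the injections.

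**Working it through.** **Order of events.** Items 5.b, 16.e and 17.e together give: enroll, randomise, move, position and monitor, sedate and prepare the skin, scan, then inject or not. Item 17 makes everything from positioning to scan common to both arms. The latest workable point for allocation is therefore after the scan, immediately before the first injection.

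**The plan's own power figure.** Inputs from the power paragraph: difference 3, SD 3, 50 per group, alpha 0.05 (two-sided assumed, as sidedness is not stated).

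- Standard error of the difference = 3 × √(2/50) = 0.60.
- Power = Φ(3/0.60 − 1.96) = Φ(3.04) = 99.9%, against the stated 95% or so.

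The mismatch is a separate matter. Here it means only that plausible losses hardly touch power.

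**Assumptions.** The documents give no rate of unplaceable blocks. Let f be the fraction of the block arm affected, and k the number of points by which those patients would score worse than the rest. Main range: f = 5% to 10%, k = 1.5. In 50 block patients this is 2.5 to 5 patients. The chance of at least one is 1 − (1 − f)^50 = 92.3% or 99.5%, which only restates the assumed rate.

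**If they are dropped from the block arm only.** Suppose the block has no effect and the other patients have mean m. The full control arm has mean m + f × k; the remaining block arm has mean m. The bias is f × k in favour of the block.

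| f | k | Bias (points) | Two-sided type I error |
|---|---|---|---|
| 5% | 1.5 | 0.075 | 5.2% |
| 10% | 1.5 | 0.15 | 5.7% |
| 10% | 2 | 0.20 | 6.2% |
| 20% | 3 | 0.60 | 15.6% |

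For f = 10%, k = 1.5: 45 block patients remain, the standard error is 3 × √(1/50 + 1/45) = 0.616, and the shift is 0.15/0.616 = 0.243. Then Φ(−1.96 + 0.243) + Φ(−1.96 − 0.243) = 5.7%. The last row is an extreme, shown only to bound the range. If affected patients would have scored better rather than worse, the bias would run against the block.

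**If they are kept in the block arm, untreated.** Exclusion bias is zero and the difference becomes 3 × (1 − f). The power figures include the extra variance from mixing treated and untreated patients.

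| f | Expected difference | Power |
|---|---|---|
| 5% | 2.85 | 99.7% |
| 10% | 2.70 | 99.3% |
| 20% | 2.40 | 97.1% |

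**If allocation follows the scan.** Patients with an unidentifiable muscle enter neither arm, so that source contributes neither exclusion bias nor dilution.

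**The case against.** The strongest reply is that the real gap is the missing analysis set. One sentence committing to analysis of all randomised patients as assigned would set the exclusion bias to zero without touching the workflow. That is correct for the bias. It does not keep the allocation from those who sedate and scan, and only a later opening does that.

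Several stronger readings are tempting, and the documents do not support them:

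- **That patients whose block is impossible are lost.** Nothing says they are dropped. They can still have surgery and report pain, and Item 17, part B, collects postoperative data in both groups.
- **That cancellations, withdrawals or poorly tolerated sedation are one-sided.** These precede the injections and patients are blinded, so they should fall on both arms alike. They cost data rather than favour an arm. Only the unusable scan is specific to one arm.
- **That dilution is a bias.** Keeping untreated patients in their assigned arm is ordinary as-randomised analysis.
- **That having no allowance above 100 threatens power.** On the plan's own inputs it does not.
- **That later allocation removes every problem.** Difficulty at needle placement after a good scan, failed analgesia (a risk listed in Item 19.a) and later cancellations still follow randomisation.

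It is also fair to say that the bias on the main assumptions is small: 0.075 to 0.15 points is about 0.13 to 0.25 of the 0.60 standard error.

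**Conclusion.** The point holds in a limited form. Allocation comes before steps that do not need it. This lets sedation and scan judgements be made with knowledge of the arm, and the undefined analysis set leaves one-sided exclusion possible. A reader might infer that the plan will lose patients from the block arm; the documents neither say so nor rule it out.

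The exclusion bias is about 0.08 to 0.15 points on a 0-10 scale if 5% to 10% of block patients are dropped with a 1.5-point penalty. Both inputs are assumptions. The effect of arm-aware sedation cannot be sized from the documents. The case for acting is that the change is cheap and closes both openings; the present sequence need not invalidate the trial.

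**What to change.** **Change.**

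- In Items 5.b and 16.e and the Item 17.e table, state that a concealed allocation is opened after positioning, sedation, skin preparation and scan have been done in the same way for every patient, once the operator has recorded whether the muscle was identified, and immediately before the injections.
- State that patients who stop before this point are not randomised and do not count toward the 100.
- In the Statistical Considerations, state that all randomised patients are followed to 48 hours and analysed as randomised, including those whose block then cannot be placed or fails. This clause is essential, because later allocation does not cover failures after it is opened.
- Reconcile two conflicts in the same revision. Item 5.b uses a block area, while Item 17 gives the block in pre-operative holding. Items 16.c and 16.h enroll on the day of surgery, while Item 21.k describes further days between consent and any study procedure.

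**Cost.** An existing 5-minute step moves to a point where the patient is already sedated and positioned. The block syringe must be ready for patients who turn out to be controls. A few consented patients will be sedated and scanned for the study but not randomised, so slightly more must be approached. The result will apply to patients in whom the muscle can be identified, and the report should say so.
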